7.3. Pharmacodynamic Analyses

7.3.1. Overview of Planned Pharmacodynamic Analyses

The PD analyses will be based on the PD population, unless otherwise specified.

[Table 5](#) provides an overview of the planned PD analyses, with full details being presented in [Appendix 10](#): List of Data Displays.

Table 5 Overview of Planned Pharmacodynamic Analyses

Display Type	Untransformed													
	Absolute							Change from Baseline						
	Stats Analysis			Summary		Individual		Stats Analysis			Summary		Individual	
	T	F	L	T	F	F	L	T	F	L	T	F	F	L
PD Concentrations				Y	Y ^{[1][2]}	Y ^[1]	Y							
PD Parameters				Y	Y		Y							

NOTES :

- T = Table, F = Figure, L = Listing, Y = Yes display generated.
- Stats Analysis = Represents TFL related to any formal statistical analyses (i.e. modelling) conducted.
- Summary = Represents TFL related to any summaries (descriptive statistics) of the observed raw data.
- Individual = Represents FL related to any displays of individual subject observed raw data.

^[1] Linear and Semi-Logarithmic plots will be created on the same display.

^[2] Separate mean and median plots will be generated.

7.3.1.1. Pharmacodynamic Parameters**7.3.1.1.1. Deriving Pharmacodynamic Parameters**

- Although erythropoietin (EPO) is an endogenous substance, the plasma concentrations of erythropoietin will not be corrected for baseline endogenous levels. Pharmacodynamic analysis will be performed on uncorrected (absolute erythropoietin concentrations) data only.
- Maximum observed erythropoietin concentration (C_{max}, EPO), Time of the maximum observed erythropoietin concentration (T_{max}, EPO) and area under the concentration-time curve from time zero (pre-dose) to the last time of quantifiable erythropoietin concentration [AUC (0-t, EPO)] will be listed and summarised if data is available.
- Pharmacodynamic parameters described in [Table 6](#) will be determined from plasma absolute erythropoietin concentration-time data as data permits.

Table 6 Derived Pharmacodynamic Parameters

Parameter	Parameter Description
C _{max} , EPO	Maximum observed EPO concentration
T _{max} , EPO	Time of the maximum observed EPO concentration
AUC (0-t, EPO)	Area under the concentration-time curve from time zero (pre-dose) to the last time of quantifiable erythropoietin concentration

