2.2. Study Design

Overview of Study Design and Key Features	
Design Features	
A phase 1, open-label, non-randomized, parallel group, single-dose adaptive study in adults with moderate (Part 1) and either mild or severe (Part 2) hepatic impairment and matched, healthy control participants with normal hepatic function.
 
Part 1:
 
Part 1 will include 2 cohorts. Cohort 1 includes participants with moderate hepatic impairment, and Cohort 2 includes matched healthy control participants.
 
Healthy control participants (n=8) will be matched in gender, age (± 10 years), and BMI ($\pm 15\%$) to participants with moderate hepatic impairment (n=8; Child-Pugh score of 7-9).
 
All participants will receive 6 mg of daprodustat as a single oral dose in the fasted state.
 
Up to 16 participants (8 in each cohort, excluding possible replacements) will be recruited into Part 1 of the study.
 
Part 2:
 
Part 2 will include 2 cohorts. Cohort 3 includes participants with either mild or severe hepatic impairment, and Cohort 4 includes matched healthy control participants.
 
Healthy control participants (n=8) will be matched in gender, age (± 10 years), and BMI ($\pm 15\%$) to participants with either mild impairment (Child-Pugh score of 5-6) or participants with severe impairment (Child-Pugh score of 10-13) (n=8).
 
All participants will receive 6 mg of daprodustat as a single oral dose in the fasted state.
 
Up to 16 participants (8 in each cohort, excluding possible replacements) will be recruited into Part 2 of the study.
 
All participant's total involvement with the study will be up to 7 weeks.

Dosing	
Part 1
 
All participants will be administered 6 mg of daprodustat as a single oral dose, with assessments conducted for up to 48 h post dosing (Please refer to Appendix 2)

Overview of Study Design and Key Features	
	
Part 2
 
If conducted, all participants will be administered 6 mg of daprodustat as a single oral dose, with assessments conducted for up to 48 h post dosing.

Treatment Assignment	
 • Part 1 consists of up to 16 participants (8 in each cohort, excluding possible replacements). • Part 2 consists of up to 16 participants (8 in each cohort, excluding possible replacements). • All participants will receive the same treatment of a single oral 6 mg dose of daprodustat.

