4. ANALYSIS POPULATIONS

Population	Definition / Criteria	Endpoint(s) Evaluated
Screened Population	
 All participants who were screened will be considered for this population. This population will be used for summarizing screening status. 	
 Screen Failure
Enrolled Population	
 All participants who were successfully screened and enrolled for the trial and for whom a record exists on the study database. This population will be used for summarize number of subjects by Country and Site ID and age ranges. 	
 Study Population
Safety Population	
 All participants who received at least one dose of study medication. This will be the primary population for the safety analyses. 	
 Study Population Safety
PK Population	
 All participants in the 'Safety Population' for whom a PK sample has been obtained and analyzed will be included in the PK population. This population will be used in the evaluation of PK data. PK samples that may be affected by protocol deviations will be reviewed by the study team to determine whether or not the sample will be excluded from the analyses of PK data. 	
 PK
PD Population	
 All participants in the 'Safety Population' who had at least 1 PD assessment. PD samples that may be affected by protocol deviations will be reviewed by the study team to determine whether or not the sample will be excluded from the analyses of PD data. 	
 PD

NOTES:

- Please refer to [Appendix 10](#) which details the population to be used for each display being generated.

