7.2.1.2.2. Statistical Analysis of Pharmacokinetic Parameters

For each of the parameters AUC (AUC(0-∞), AUC (0-t) and %AUCex)-total and free, t_{1/2}, T_{max} and C_{max}-total and free the following summary statistics will be calculated and tabulated by each cohort:

- **Untransformed Data:** N, n, arithmetic mean, 95% confidence interval (CI) for the arithmetic mean, SD, median, minimum and maximum.
- **Log_e-transformed Data:** Geometric mean, 95% CI for the geometric mean, SD of log_e-transformed data and between subject geometric coefficient of variation (%CVb).
- If data suggest appreciable differences existing in the results obtained based on the observed total and unbound daprodustat PK plasma concentration data, and if deemed appropriate, the bound fraction (1-Fu) at 3 h, 12 h and 24 h will be analysed using paired t-test comparing 12h versus 3h, 24 h versus 3h and 24 h versus 12h.

The following PK statistical analyses will only be performed, if sufficient data is available (i.e. if subjects have well defined plasma profiles). Pharmacokinetic analysis and Statistical analyses of the PK parameter data will be the responsibility of PPD.

Planned Pharmacokinetic Statistical Analyses
Endpoint(s)

 • Plasma primary PK endpoints include AUC (0-t), AUC (0-∞), Cmax and t_{1/2}, as data permit
Model Specification

 • The log-transformed AUC(0-t), AUC (0-∞), Cmax and t_{1/2} values for daprodustat and metabolites will be analyzed separately using analysis of variance (ANOVA) as appropriate to the study design, fitting a fixed effect term for cohort. Point estimates and 90% CIs for the differences of interest (hepatically impaired versus healthy participants) will be constructed using the residual variance.
Model Checking & Diagnostics

 • Refer to Appendix 8 : Model Checking and Diagnostics for Statistical Analyses.
Model Results Presentation

 • Statistical analysis by ANOVA will be presented in tabular format with geometric mean ratios for the hepatically impaired versus healthy participants and 90% CI for the ratios of AUC (0-t), AUC (0-∞), Cmax and t_{1/2} for daprodustat and metabolites.

Planned Pharmacokinetic Statistical Analyses
Endpoint(s)

 • Tmax
Model Specification

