10.6. Appendix 6: Premature Withdrawals & Handling of Missing Data

10.6.1. Premature Withdrawals

Element	Reporting Detail
General	
 • A completed subject is one who has completed all phases of the study including the follow-up visit. • Withdrawn subjects may be replaced in the study. • All subjects who withdraw prematurely from the study will be documented and the reason for their withdrawal recorded in the final Clinical Pharmacology Study Report (CPSR). • All available data collected up until the point of withdrawal, and the follow-up visits will be used in the analyses and will be listed and all available planned data will be included in the summaries according to the populations defined in Section 4 unless otherwise specified.

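### AUC(0-t, EPO) has no common end time, so an EPO profile that stops before 48 h is averaged with 48 h AUCs under one label

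*SAP*

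**What the plan says.** The references are to the amended SAP, which is based on the protocol dated 15-Nov-2017.

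- **Definition.** Section 7.3.1.1.1 and Table 6 give the parameter as the "area under the concentration-time curve from time zero (pre-dose) to the last time of quantifiable erythropoietin concentration". Protocol sections 1 and 4 define the secondary endpoint in the same way. Neither document sets a common end time.
- **No baseline correction.** Section 7.3.1.1.1 calls EPO endogenous and states that "plasma concentrations of erythropoietin will not be corrected for baseline endogenous levels". Parameters "will be determined from plasma absolute erythropoietin concentration-time data as data permits", with no minimum sampling time or number of points.
- **Planned sampling.** Section 2.2 describes dosing "with assessments conducted for up to 48 h post dosing". The schedule in Appendix 2 takes EPO samples from pre-dose to 48 h, with 12, 24, 36 and 48 h as the last four.
- **Who is summarised.** Under section 4 the PD population is everyone in the Safety Population "who had at least 1 PD assessment". Table 4.2 summarises the EPO parameters on that population.
- **Withdrawals.** Section 10.6.1 states: "All available data collected up until the point of withdrawal, and the follow-up visits will be used in the analyses". It adds that "all available planned data will be included in the summaries according to the populations defined in Section 4". Withdrawn participants may be replaced, but nothing removes their values. Section 10.6.2.4 rules out imputation.
- **A guard for PK only.** Section 7.2.1.2.2 states: "The following PK statistical analyses will only be performed, if sufficient data is available (i.e. if subjects have well defined plasma profiles". The PD section has no counterpart.

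**The concern.** AUC(0-t) for a drug that is eliminated levels off, so a missing late sample usually costs little area. Uncorrected EPO does not behave like that. The baseline alone adds the same area every hour. If EPO remains quantifiable throughout, the end point is simply the last usable sample: 48 h for a completer, and earlier for anyone who left or lost late samples. An AUC(0-12) and an AUC(0-48) would then sit in one mean under one name.

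At stake is one of the three parameters serving the secondary PD objective. With about 8 participants per cohort, summarised by the arithmetic mean, its 95% CI, SD, median and range, one short profile lowers the mean, widens the SD and may become the minimum.

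**Working it through.** **Plan's own figure.** The documents give no EPO concentrations, variability or expected precision. The only design figure is for daprodustat AUC in protocol section 10.2.1: exp(±t(0.95, 14 df) × SD × √(2/8)) = exp(±1.761 × 0.402 × 0.5) = (0.70, 1.43). It reproduces, but it does not bear on EPO.

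**Inputs.** Sampling times come from SAP Appendix 2, and the cohort size of 8 from protocol section 10.2.1. The EPO profile is an assumption: baseline 1, a linear rise to m times baseline at 10 h, a linear fall back to baseline at 24 h, then flat to 48 h, with m = 1 (flat), 2 or 4. EPO is assumed quantifiable throughout. Table 6 gives no AUC rule for EPO, so the linear trapezoid is used first. It is exact here because 10 h and 24 h are sampling times.

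**Areas, in baseline × h**

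- AUC(0-48) = 48 + ½ × 24 × (m − 1) = 48 + 12(m − 1).
- AUC(0-12) = 12 + 5(m − 1) + 1.857(m − 1). The term 5 is ½ × 10. The term 1.857 is 2 × (1 + 12/14)/2, the stretch from 10 to 12 h.
- AUC(0-24) = 24 + 12(m − 1).
- AUC(0-36) = 36 + 12(m − 1).

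**Share of AUC(0-48), r, and fall in a cohort mean of 8, (1 − r)/8**, taking the other seven to have similar 48 h AUCs:

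| Last sample | m = 1 | m = 2 | m = 4 | Fall in mean |
|---|---|---|---|---|
| 12 h | 12/48 = 25% | 18.86/60 = 31% | 32.57/84 = 39% | 9.4%, 8.6%, 7.7% |
| 24 h | 24/48 = 50% | 36/60 = 60% | 60/84 = 71% | 6.3%, 5.0%, 3.6% |
| 36 h | 36/48 = 75% | 48/60 = 80% | 72/84 = 86% | 3.1%, 2.5%, 1.8% |

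With the linear-up/log-down rule that SAP Table 4 uses for the drug, m = 4 at 12 h becomes 32.56/80.80 = 40%, and the fall becomes (1 − 0.403)/8 = 7.5%. The other entries move by about one point or less.

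**Sensitivity to shape.** With assumed peaks at 6, 8 or 12 h of 1.5 to 10 times baseline, the shares are 26-58% at 12 h, 55-83% at 24 h and 78-93% at 36 h. The falls in the mean are about 5-9%, 2-6% and 1-3%.

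**With a replacement.** Eight completers plus one 12 h exit make nine values. The fall is (1 − 0.25)/9 = 8.3% for a flat profile and (1 − 0.403)/9 = 6.6% for m = 4.

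**The case against.** **The trigger should be rare.** This is a single dose in an inpatient unit, with discharge at 48 h, the time of the last EPO sample. Hepatically impaired participants must have been clinically stable for a month before screening. If everyone is sampled to 48 h with quantifiable EPO, a common interval changes no value. This stands, and it is the main reason to rank the point low.

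**The consequence is limited.** SAP Table 5 plans no statistical analysis of PD data, the median and range are reported beside the mean, and a short profile would be visible in Figure 4.1 and Listings 46 and 47. The shift is also small against sampling error. If the EPO CV were 30-60% (an assumption), the 95% CI of a mean of 8 would be about ±2.365/√8 × CV, or ±25% to ±50%. This stands too.

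**The SAP leaves some discretion.** Derivation depends on what the data permit, PD samples affected by deviations are reviewed, and the impact of major timing deviations is to be assessed. This helps only in part. A 12 h profile does permit an AUC(0-t). The review concerns samples, not incomplete profiles, and excluding a late sample would itself move the end point earlier. Discretion without a rule also means deciding after the data are seen, in an open-label study.

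**The endpoint is in the protocol.** A common-interval AUC is therefore more than a wording change to the SAP. This is correct and is reflected in the fix.

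**Conclusion.** The point holds as a minor, cheap improvement. Followed as written, the SAP averages EPO AUCs over unequal intervals whenever a profile ends before 48 h. One such profile among 8 costs the cohort mean about 7.5-9% for a last sample at 12 h, 4-6% at 24 h and 2-3% at 36 h. These figures rest on assumed profile shapes and on EPO staying quantifiable. The internal non-compartmental guidance that the SAP cites is not available here; for PD concentrations the SAP invokes it only for non-quantifiable values.

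A reader might infer two stronger things, and the documents support neither:

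- **A bias between cohorts.** One could suppose that ill participants leave sooner, so that the impaired cohort's EPO exposure would be understated. The documents give no dropout assumption for either group, so no direction or imbalance can be claimed.
- **The same problem in Cmax, EPO and Tmax, EPO.** These are affected only if sampling stops before the peak. Nothing in the documents shows that as a practical problem, and no extra rule for them is warranted.

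**What to change.** In SAP section 7.3.1.1.1 and Table 6, define the summarised parameter over a common interval, AUC(0-48 h, EPO), for participants sampled to 48 h, and use it in Table 4.2. Keep shorter AUC(0-t, EPO) values in Listing 47, flagged as incomplete and with their end time. Leave Cmax, EPO and Tmax, EPO as they are.

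Record this as a declared change from the secondary endpoint in protocol sections 1 and 4. The SAP written for the 23-May-2017 protocol declared its EPO endpoint change in its section 2.1; the amended SAP has no such section, so a short one is needed.

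No new samples or procedures are required, and the value is unchanged for everyone with quantifiable EPO at 48 h. The cost is that n for the EPO AUC falls by one for each incomplete profile. That includes anyone missing only the 48 h sample, whose value to 36 h would still hold about 75-86% of the area under the assumed profiles.

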8. SAFETY ANALYSES

The safety analyses will be based on the “Safety” population, unless otherwise specified.

8.1. Overview of Planned Adverse Events Analyses

Adverse Events will be coded using Medical Dictionary for Regulatory Activities (MedDRA) central coding dictionary and summarized by cohort.

Counting of AEs will be based on the number of subjects – not the number of AEs. For example, if a subject experiences the same AE (i.e. same preferred term) more than once, they are counted only once under the count for the preferred term. If a subject experiences more than one AE in a particular system organ class (SOC), they will only be included once in the count for the SOC, but will appear in the count for each appropriate preferred term within the SOC. Therefore, the sum of the numbers of subjects with each preferred term event within a SOC may exceed the total number of subjects with at least one event.

[Table 7](#) provides an overview of the planned analyses, with further details of data displays being presented in [Appendix 10](#): List of Data Displays.

Table 7 Overview of Planned Adverse Event Analyses

Endpoint / Parameter/ Display Type	Absolute		
	Summary		Individual
	T	F	L
Adverse Events (AEs)			
All AEs	Y		Y
Serious AEs	Y		Y
Drug Related AEs	Y		Y
AEs leading to withdrawal	Y		Y
Summary of Common (>=25%) Non-serious Adverse Events by System Organ Class and Preferred Term	Y		
Serious Adverse Events by System Organ Class and Preferred Term (Number of Subjects and Occurrences)	Y		
Relationship Between System Organ Class and Verbatim Text			Y
Subject Numbers for Individual Adverse Events			Y
AEs of special interest ^[1]			Y

NOTES:

- T = Table, F = Figures, L = Listings, Y = Yes display generated
- Summary = Represents TF related to any summaries (i.e. descriptive statistics) of the observed raw data.
- Individual = Represents FL related to any displays of individual subject observed raw data.

^[1] Conditional displays, if data is available listing will be generated.

8.2. Overview of Planned Clinical Laboratory Analyses

Table 8 provides an overview of the planned analyses, with further details of data displays being presented in Appendix 10: List of Data Displays.

Table 8 Overview of Planned Clinical Laboratory Analyses

Endpoint / Parameter/ Display Type	Absolute			Change from BL		
	Summary		Individual	Summary		Individual
	T	F	L	T	F	L
Chemistry						
Clinical Chemistry	Y		Y	Y		
Clinical Chemistry (Values Outside the PCI Range)			Y			
Haematology						
Haematology	Y		Y	Y		
Haematology (Values Outside the PCI Range)			Y			
Urinalysis						
Urinalysis			Y			

NOTES:

- T = Table, F = Figures, L = Listings, Y = Yes display generated
- Summary = Represents TFL related to any summaries (i.e. descriptive statistics) of the observed raw data.
- Individual = Represents FL related to any displays of individual subject observed raw data.

8.3. Overview of Planned Other Safety Analyses

Table 9 provides an overview of the planned analyses, with further details of data displays being presented in Appendix 10: List of Data Displays

Table 9 Overview of Planned Other Safety Analyses

Endpoint / Parameter/ Display Type	Absolute			Change from BL		
	Summary		Individual	Summary		Individual
	T	F	L	T	F	L
ECG						
ECG Findings	Y		Y			
ECG Values	Y		Y	Y		
ECG Values Outside the PCI Range			Y			
Maximum QTc Values Post-Baseline Relative to Baseline by Category				Y		
Maximum Increase in QTc Values Post-Baseline Relative to Baseline by Category				Y		
Vital Signs						
Vitals Values	Y		Y	Y		
Vital Signs Measurements Outside the PCI Range			Y			

NOTES:

- T = Table, F = Figures, L = Listings, Y = Yes display generated, PCI = Potential Clinical Importance
- Summary = Represents TFL related to any summaries (i.e. descriptive statistics) of the observed raw data.
- Individual = Represents FL related to any displays of individual subject observed raw data.

10. APPENDICES

Section	Appendix
RAP Section 4: Analysis Populations	
Section 10.1	Appendix 1 : Protocol Deviation Management
RAP Section 5 : General Considerations for Data Analyses & Data Handling Conventions	
Section 10.2	Appendix 2 : Time and Events
Section 10.3	Appendix 3 : Treatment States
Section 10.4	Appendix 4 : Data Display Standards & Handling Conventions 
 • Study Treatment & Sub-group Display Descriptors • Baseline Definitions & Derivations • Reporting Process & Standards
Section 10.5	Appendix 5 : Derived and Transformed Data 
 • General • Study Population • Safety • Pharmacokinetic • Pharmacodynamic
Section 10.6	Appendix 6 : Premature Withdrawals & Handling of Missing Data 
 • Premature Withdrawals • Handling of Missing Data 
 ○ Handling of Missing Dates ○ Handling of Partial Dates
Section 10.7	Appendix 7 : Values of Potential Clinical Importance 
 • Laboratory Values • ECG • Vital Signs
Section 10.8	Appendix 8 : Model Checking and Diagnostics for Statistical Analyses
Other RAP Appendices	
Section 10.9	Appendix 9 Abbreviations & Trade Marks
Section 10.10	Appendix 10 : List of Data Displays

10.1. Appendix 1: Protocol Deviation Management

There are no pre-defined categories leading to exclusion from the PK population but all protocol deviations will be reviewed on a case-by-case basis.

No subjects will be excluded from the safety population.

10.2. Appendix 2: Time & Events

10.2.1. Protocol Defined Time & Events

Procedure	Screening ¹	Day -1	Pre-Dose	0 h	0.5 h	1 h	1.5 h	2 h	3 h	4 h	6 h	8 h	10 h	12 h	24 h	36 h	48 h	Follow-up ²
Informed Consent	X																	
Inclusion & Exclusion Criteria	X	X																
Demography	X																	
Full physical exam	X																	
Medical history	X																	
Past/current medications	X																	
Laboratory assessments ³	X																X	X
Drug/Alcohol Screen	X	X																
12-lead ECG	X	X															X	X
Vital Signs and Weight	X	X															X	X
Pregnancy Test	X ⁴	X ⁴																
Females only: Estrogen and FSH ⁵	X																	

CONFIDENTIAL

200231

Procedure	Screening ¹	Day -1	Pre-Dose	0 h	0.5 h	1 h	1.5 h	2 h	3 h	4 h	6 h	8 h	10 h	12 h	24 h	36 h	48 h	Follow-up ²
Admission to Unit		X																
Brief Physical Exam		X															X	X
Administration of daprodustat				X														
PK blood sampling			X		X	X	X	X	X	X	X	X	X	X	X	X	X	
Protein binding sample			X						X					X	X			
EPO blood sampling			X		X	X	X	X	X	X	X	X	X	X	X	X	X	
Adverse Events Assessment	X	X	X	X	X	X	X	X	X	X	X	X	X	X	X	X	X	X
Review Concomitant Medications		X	X												X		X	X
Discharge from Unit																	X	

¹ All participants will undergo screening assessments within 28 days of enrolment.

² A follow-up visit will occur 10-14 days after the dose of study treatment.

³ Laboratory assessment guidance can be found in Protocol Appendix 3.

⁴ For women of childbearing potential that are not using an approved method of contraception (see Protocol Appendix 6), one negative pregnancy test between Day -7 and Day -4 AND another negative pregnancy test on Day -1 is required. Additional guidance can be found in Protocol Section 9.5.5.

⁵ All females are to have estrogen and FSH measured at screening.

